2. OBJECTIVES

This trial will assess the safety, tolerability and efficacy of a treat and extend management protocol for DME. Patients will be enrolled into one of three treatment groups: (1) monthly intravitreal injections of 0.3 mg ranibizumab (Monthly Cohort, 30 eyes); (2) monthly intravitreal injections of 0.3 mg ranibizumab for 4 visits, followed by a “Treat and EXtend” protocol based on pre-specified criteria of disease activity (T-REX cohort, 60 eyes); (3) monthly intravitreal injections of 0.3 mg ranibizumab for 4 visits combined with adjunctive Guided focal Laser macular photocoagulation to microaneurysms at week 4 and then every 3 months if leakage is present on fluorescein angiography, followed by a treat and extend protocol based on pre-specified criteria of disease activity (GILA cohort, 60 eyes).

2.1 Primary Objective

- Mean change in ETDRS visual acuity at 24 months (week 92 – week 107) from Day 0.

2.2 Secondary Objectives

- Incidence and severity of adverse events (ocular and non-ocular).
- Total number of intravitreal injections required during each year of the study period (week 52, week 104, and week 156). In a separate proof of concept analysis, the number of intravitreal injections in the TREX and GILA cohorts over the 36-month study period will be compared with that of the other two cohorts ($p = 0.20$).
- Total number of office visits and imaging studies performed during each year of the study period.
- Mean change in central foveal thickness per SD-OCT from randomization to 12 months (week 46 – week 57), randomization to 24 months (week 92 – week 107), and randomization to 36 months (week 156).
- Percentage of eyes gaining or losing 3 lines of vision or more and 1 line of vision or more at 6 months (week 22 – week 29), 12 months (week 46 – week

57), 18 months (week 70 – week 85), 24 months (week 92 – week 107), and 36 months (week 156) from Day 0.

- Noninferiority comparison (margin of 9 letters) of mean change in ETDRS vision from Day 0 to 24 months (week 92 – week 107) between the three study groups.
- The percentage of eyes which show progression of proliferative diabetic retinopathy requiring panretinal photocoagulation and/or pars plana vitrectomy over the 36-month study period.
- The percentage of eyes in the TREX and GILA cohorts who are eligible to begin the extension phase after 4 treatment visits.
- For TREX and GILA Cohorts, the time to achieve a “Secondary or Tertiary Baseline” retinal thickness.
- Percentage of eyes in each cohort that have shown a two-step change (increase and decrease) in diabetic retinopathy at 24 months and 36 months from day 0.

3. STUDY DESIGN

3.1 DESCRIPTION OF THE STUDY

This is an open-label, phase I/II trial, which will assess the safety, tolerability and efficacy of a treat and extend management protocol for DME. Eyes which meet screening criteria will be enrolled into one of three treatment groups: (1) monthly intravitreal injections of 0.3 mg ranibizumab (Monthly Cohort, 30 eyes); (2) monthly intravitreal injections of 0.3 mg ranibizumab for 4 visits, followed by a “Treat and Extend” protocol based on pre-specified criteria of disease activity (T-REX cohort, 60 eyes); (3) monthly intravitreal injections of 0.3 mg ranibizumab for 4 visits combined with adjunctive Guided focal Laser photocoagulation to microaneurysms at week 4 and then every 3 months if leakage is present on fluorescein angiography, followed by a treat and extend protocol based on pre-specified criteria of disease activity (GILA cohort, 60 eyes).

Randomization Scheme:

All eyes which satisfy all inclusion/exclusion criteria will be randomized 1:2:2 into the Monthly:TREX:GILA Cohorts.

3 Treatment arms:

1. Monthly Cohort (30 eyes): Monthly intravitreal injections of 0.3 mg ranibizumab for 36 months, unless they meet pre-specified criteria for PRN treatment (indicated below). Treatment will begin at Day 0 and

subsequent study visits should be scheduled to occur every 28 (± 7) days relative to the date of the first injection. Dosing should not occur earlier than 21 days after previous treatments.

Starting at week 104, study eyes will have the opportunity to undergo treatment on a pro re nata (PRN) basis. Thus, eyes who have a central subfield thickness (CST) ≤ 325 microns at the week 104 visit, will not be given treatment at week 104. Eyes will continue to be seen every 4 weeks and will be given an intravitreal injection of ranibizumab 0.3 mg only if the CST is > 325 microns. Eyes will also receive treatment if there is a > 5 letter loss due to DME (compared to the vision at week 104), regardless of thickness on OCT.

Subjects will be evaluated for focal laser treatment at week 116, week 128, week 140, and week 152. If the subject has received ≥ 2 intravitreal injections of ranibizumab within the prior 90 day period, then fluorescein angiography will be performed and focal laser treatment will be applied to any leaking microaneurysms. If the patient does not meet this criteria for focal laser treatment, then fluorescein angiography and focal laser treatment will be deferred and reassessed at the subsequent laser evaluation visit. Focal laser treatment and focal laser re-treatment will be administered no more than once every 90 days.

Focal laser therapy will be applied to all leaking microaneurysms on fluorescein angiography. Focal laser therapy will not be applied if significant macular ischemia is present involving the foveal avascular zone (once this has been determined additional fluorescein angiography and focal laser treatment planning should not be performed as the subject will no longer be eligible for focal laser treatment). Focal laser will also not be applied if treatment is considered too close to the foveal avascular zone or to macular edema not related to DME (cystoid macular edema, etc.). If no microaneurysms are present on fluorescein angiography, then focal laser therapy should be deferred and reassessed with repeat fluorescein angiography at the first visit that occurs after 90 days.

2. TREX Cohort (60 eyes): Monthly intravitreal injections of 0.3 mg ranibizumab for four (4) visits. If the central foveal thickness is ≤ 325 μm at the fourth visit (Week 12) then the baseline retinal thickness will be recorded, the eye will receive 0.3 mg ranibizumab and the study eye will begin the extension phase of the study. For all subsequent visits in the extension phase, appropriate changes to the treatment interval with 0.3 mg ranibizumab (i.e. extend, maintain, reduce) will be made based on pre-specified SD-OCT criteria (SEE TREATMENT INTERVAL DETERMINATION). Treatment is rendered at

every visit, no earlier than 7 days before the target date and no later than 7 days after the target date, but the time between visits is individualized based on each subject's response to treatment. Dosing should not occur earlier than 21 days after previous treatments.

If the central foveal thickness is $> 325 \mu\text{m}$ at week 12, the patient will continue to receive monthly intravitreal injections of 0.3 mg ranibizumab until the central foveal thickness is $\leq 325 \mu\text{m}$. Once the central foveal thickness is $\leq 325 \mu\text{m}$, the study eye will begin the extension phase of the study.

Starting at week 104, study eyes will have the opportunity to undergo treatment on a pro re nata (PRN) basis. Thus, eyes who have a central subfield thickness (CST) ≤ 325 microns at the week 104 visit, will not be given treatment at week 104. Starting at week 104, eyes will be seen every 4 weeks and will be given an intravitreal injection of ranibizumab 0.3 mg only if the CST is > 325 microns. Eyes will also receive treatment if there is a > 5 letter loss due to DME (compared to the vision at week 104), regardless of thickness on OCT.

Subjects will be evaluated for focal laser treatment at week 116, week 128, week 140, and week 152. If the subject has received ≥ 2 intravitreal injections of ranibizumab within the prior 90 day period, then fluorescein angiography will be performed and focal laser treatment will be applied to any leaking microaneurysms. If the patient does not meet this criteria for focal laser treatment, then fluorescein angiography and focal laser treatment will be deferred and reassessed at the subsequent laser evaluation visit. Focal laser treatment and focal laser re-treatment will be administered no more than once every 90 days.

Focal laser therapy will be applied to all leaking microaneurysms on fluorescein angiography. Focal laser therapy will not be applied if significant macular ischemia is present involving the foveal avascular zone (once this has been determined additional fluorescein angiography and focal laser treatment planning should not be performed as the subject will no longer be eligible for focal laser treatment). Focal laser will also not be applied if treatment is considered too close to the foveal avascular zone or to macular edema not related to DME (cystoid macular edema, etc.). If no microaneurysms are present on fluorescein angiography, then focal laser therapy should be deferred and reassessed with repeat fluorescein angiography at the first visit that occurs after 90 days.

3. GILA Cohort (60 eyes): Monthly intravitreal injections of 0.3 mg ranibizumab for four visits combined with Guided LAser (GILA) photocoagulation to all microaneurysms in the area of DME at the second visit (Week 4). Fluorescein angiography is to be repeated approximately every 3 months (the first visit that occurs ≥ 90 days from the preceding fluorescein angiography visit). Guided laser will be repeated at those visits if leakage is present from microaneurysms.

If the central foveal thickness is $\leq 325 \mu\text{m}$ at Week 12 then the baseline retinal thickness will be recorded, the eye will receive 0.3 mg ranibizumab, and the study eye will begin the extension phase of the study. In the extension phase, appropriate changes to the treatment interval with 0.3 mg ranibizumab (i.e. extend, maintain, reduce) will be made based on pre-specified SD-OCT criteria (SEE TREATMENT INTERVAL DETERMINATION). Treatment is rendered at every visit, no earlier than 7 days before the target date and no later than 7 days after the target date, but the time between visits is individualized based on each subject's response to treatment. Dosing should not occur earlier than 21 days after previous treatments.

If the central foveal thickness is $> 325 \mu\text{m}$ at week 12, then the patient will continue to receive monthly intravitreal injections of 0.3 mg ranibizumab and possible guided laser photocoagulation, approximately every 3 months until the central foveal thickness is $\leq 325 \mu\text{m}$. Once the central foveal thickness is $\leq 325 \mu\text{m}$, then the study eye will begin the extension phase of the study.

Starting at week 104, study eyes will have the opportunity to undergo treatment on a pro re nata (PRN) basis. Thus, eyes who have a central subfield thickness (CST) ≤ 325 microns at the week 104 visit, will not be given treatment at week 104. Starting at week 104, eyes will be seen every 4 weeks and will be given an intravitreal injection of ranibizumab 0.3 mg only if the CST is > 325 microns. Eyes will also receive treatment if there is a > 5 letter loss due to DME (compared to the vision at week 104), regardless of thickness on OCT.

After week 104, subjects will be evaluated for focal laser treatment in the same manner as the Monthly and TREX Cohorts. Subjects will be evaluated for focal laser treatment at week 116, week 128, week 140, and week 152. If the subject has received ≥ 2 intravitreal injections of ranibizumab within the prior 90 day period, then fluorescein angiography will be performed and focal laser treatment will be applied to any leaking microaneurysms. If the patient does not meet this criteria for focal laser treatment, then fluorescein angiography and focal laser treatment will be deferred and reassessed at the subsequent laser evaluation visit. Focal

laser treatment and focal laser re-treatment will be administered no more than once every 90 days.

Focal laser therapy will be applied to all leaking microaneurysms on fluorescein angiography. Focal laser therapy will not be applied if significant macular ischemia is present involving the foveal avascular zone (once this has been determined additional fluorescein angiography and focal laser treatment planning should not be performed as the subject will no longer be eligible for focal laser treatment). Focal laser will also not be applied if treatment is considered too close to the foveal avascular zone or to macular edema not related to DME (cystoid macular edema, etc.). If no microaneurysms are present on fluorescein angiography, then focal laser therapy should be deferred and reassessed with repeat fluorescein angiography at the first visit that occurs after 90 days.

Baseline Retinal Thickness Measurement for the TREX and GILA Cohorts:

For eyes which have a central foveal thickness $\leq 325 \mu\text{m}$ at week 12, a "Primary Baseline" retinal thickness will be defined as the thinnest central foveal thickness on SD-OCT over the first four visits of monthly treatment. Eyes which have a central foveal thickness $> 325 \mu\text{m}$ at week 12 will continue to receive monthly intravitreal injections of 0.3 mg ranibizumab until the central foveal thickness is $\leq 325 \mu\text{m}$, at which point their "Primary Baseline" retinal thickness will be established. Eyes in the GILA cohort will continue to receive guided laser photocoagulation to microaneurysms every 3 months if leakage is present on fluorescein angiography.

If at any point in the study period, the study eye has improved more than 20% from the primary baseline thickness for three consecutive visits and there is less than 50 microns of variability in central foveal thickness between these visits, then a "Secondary Baseline" retinal thickness will be established. This "Secondary Baseline" retinal thickness will then be used for treatment interval determinations from that point forward. If the study eye has improved more than 20% from the secondary baseline thickness for three consecutive visits and there is less than 50 microns of variability in central foveal thickness between these visits, then a "Tertiary Baseline" retinal thickness will be established. This "Tertiary Baseline" retinal thickness will then be used for treatment interval determinations from that point forward.

Treatment Interval Determination For TREX and GILA Cohorts:

Starting at Week 12, if the central foveal thickness is $\leq 325 \mu\text{m}$, then the following re-treatment criteria will be applied at all visits. Eyes with central foveal thickness $> 325 \mu\text{m}$ at week 12 will continue to receive monthly injections of 0.3 mg ranibizumab until the central foveal thickness is $\leq 325 \mu\text{m}$, at which time the following re-treatment criteria will be applied at all visits. Eyes in the GILA cohort will continue to receive guided laser photocoagulation to microaneurysms every 3 months if leakage is present on fluorescein angiography. This treatment interval determination will continue up to week 104.

Extend Interval (by 2 weeks):

1. If the central foveal thickness on SD-OCT is within $\leq 10\%$ thicker or thinner compared to baseline (primary, secondary, or tertiary baseline) retinal thickness.

Maintain Interval:

1. If the central foveal thickness is between $> 10\%$ thicker and $\leq 20\%$ thicker from the baseline retinal thickness (primary, secondary or tertiary baseline) OR
2. If the central foveal thickness is $> 10\%$ thinner from baseline retinal thickness (primary, secondary or tertiary baseline).

Reduce Interval (by 2 weeks):

1. If the central foveal thickness is $> 20\%$ thicker from baseline retinal thickness (primary, secondary or tertiary baseline).

Reduce Interval to 4 weeks:

1. If there is a loss of more than 15 letters from best previous ETDRS vision, due to DME.

Study eyes which have not met criteria allowing them to extend to greater than or equal to 6 weeks for two consecutive visits by the week 52 (hard endpoint) visit will receive a series of three intravitreal injections of ranibizumab 0.3 mg every 4 weeks regardless of SD-OCT measurement. This series of three injections every 4 weeks will begin at the first treatment visit that occurs after the 52 week hard endpoint visit. The study eye will resume treatment interval determinations based on the pre-specified criteria at the time of the third monthly intravitreal injection.

The interval between study injections will not exceed 12 weeks in year one of the study. The interval between study injections can be extended to, but not more than, 16 weeks in year two of the study.

Enrolled subjects will have ETDRS BCVA, complete ophthalmic examination and SD-OCT evaluation using Spectralis machines at each visit. Fluorescein angiography will be done in the Monthly and TREX Cohorts at baseline (screening visit) and again at week 12, week 52, and week 104 or visits closest

to. Fluorescein angiography will be done in the GILA Cohort at baseline (screening visit), week 4, and every 90 days or greater (first visit that occurs \geq 90 days from previous fluorescein angiogram). See Appendix A for schedule of events from screening visit to week 104 and Appendix A.1 for the schedule of events between week 108 and week 156.

End-Point Visits

Subjects will continue to receive study treatments according to the above treatment protocol until week 155. A “Hard End-Point Visit” will occur at week 52, week 104, and week 156. A “Biologic End-Point Visit” will occur 4 weeks after the previous injection near the 12-month time point (week 46 – week 57), 24-month time point (week 92 – week 107). Only best corrected visual acuity and SD-OCT measurements will be recorded at these endpoint visits. No study treatment will be given at these end-point visits, unless the patient has a regular study treatment visit that occurs at these time points.

Fellow eyes not enrolled into a study group that have DME during the course of the study may be treated with standard of care macular laser photocoagulation and/or intravitreal injections of 0.3 mg of ranibizumab at the investigator’s discretion. Ranibizumab will be provided by Genentech for treatment of DME in the fellow eye.

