3.3.2 Secondary Outcome Measures

- Incidence and severity of adverse events (ocular and non-ocular).
- Total number of intravitreal injections required during each year of the study period (week 52, week 104, and week 156). In a separate proof of concept analysis, the number of intravitreal injections in the TREX and GILA cohorts over the 36-month study period will be compared with that of the other two cohorts ($p = 0.20$)
- Total number of office visits and imaging studies performed during each year of the study period (week 52, week 104, and week 156).
- Mean change in central foveal thickness per SDOCT from randomization to 12 months (week 46 – week 57), randomization to 24 months (week 92 – week 107), and randomization to 36 months (week 156).
- Percentage of eyes gaining or losing 3 lines of vision or more and 1 line of vision or more at 6 months (week 22 – week 29), 12 months (week 46 – week 57), 18

months (week 70 – week 85), 24 months (week 92 – week 107), and 36 months (week 156) from Day 0.

- Noninferiority comparison (margin of 9 letters) of mean change in ETDRS vision from Day 0 to 24 months (week 92 – week 107) between the three study groups.
- The percentage of eyes which show progression of proliferative diabetic retinopathy requiring panretinal photocoagulation and/or pars plana vitrectomy over the 36-month study period.
- The percentage of eyes in the TREX and GILA cohorts who are eligible to begin the extension phase after 4 treatment visits.
- For TREX and GILA Cohorts, the time to achieve a “Secondary or Tertiary Baseline” retinal thickness.
- Percentage of eyes in each cohort that have shown a two-step change (increase and decrease) in diabetic retinopathy at 24 months and 36 months from day 0.

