Ocular morphology will be evaluated using the Heidelberg Spectralis Domain (SD) OCT on the study eye. All SD-OCT images will be captured using the

most current software. All SD-OCTs will be electronically archived at the site as part of the source documentation.

Microperimetry –

Microperimetry will be performed at the locations where a microperimeter is available on all study eyes in the TREX and GILA cohorts at screening, week 24, week 52 and week 104, or the closest visit to these time points.

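### SD-OCT software is not held fixed although TREX and GILA injection intervals depend on percentage change from a stored thickness baseline; as a minor point, the 325-micron cut-off changes its named quantity at week 104

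*Combined protocol and SAP*

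**What the plan says.** **Software.** The OCT paragraph of section 4.5.1 fixes the device (Spectralis) and asks for capture with the "most current software. All SD-OCTs will be electronically archived at the site as part of the source documentation". No section names a version, says what happens if one changes during follow-up, or calls for earlier scans to be re-read.

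**Rules up to week 104 (section 3.1, TREX and GILA).**
- Entry to the extension phase: "If the central foveal thickness is ≤ 325 μm at the fourth visit (Week 12").
- The Primary Baseline is "defined as the thinnest central foveal thickness on SD-OCT over the first four visits of monthly treatment". Eyes still above 325 microns at week 12 have it set later, once they reach the cut-off.
- Interval bands: the extend rule begins "If the central foveal thickness on SD-OCT is within" and allows 10% either side of that baseline. Between 10% and 20% thicker, or more than 10% thinner, means maintain. More than 20% thicker means reduce by 2 weeks.
- Duration: "This treatment interval determination will continue up to week 104".

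Monthly eyes are injected on a fixed schedule in this period, with no OCT criterion.

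**Rule from week 104 (section 3.1, all three cohorts).** The wording now refers to "eyes who have a central subfield thickness (CST") of 325 microns or less at week 104, which are not treated at that visit. The same cut-off then governs the 4-weekly visits, alongside a letter-loss criterion.

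**Outcome (section 3.3.2).** "Mean change in central foveal thickness per SDOCT from randomization to 12 months", and likewise to 24 and 36 months.

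**The concern.** A rule that compares today's thickness with a stored value assumes that both were produced in the same way. An instruction to use the newest software, without a lock or a re-processing rule, leaves that assumption unprotected for 36 months. If an update altered the thickness reading, the difference would be read as disease change. In TREX and GILA it could then move the next injection. Monthly eyes could not be affected in this way before week 104, so the disturbance would fall on one side of the injection-count comparison. With about three sites (section 4.1.1) and scans archived locally, updates could also arrive at different times.

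The second issue is one of definition. The same 325 microns is attached to two differently named quantities, before and from week 104, and the protocol neither defines them nor equates them. A site cannot tell from the text whether one Spectralis output is meant or two.

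**Working it through.** The plan gives no figure to reproduce. The inputs are the 10% and 20% bands and the 325-micron cut-off (section 3.1). The 300-micron baseline and the software offsets of 5, 10 and 15 microns are assumptions for illustration.

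**1. Share of the band used up by an offset.** The 10% limit is 0.10 × 300 = 30 microns and the 20% limit is 0.20 × 300 = 60 microns.

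| Assumed offset (microns) | Share of 10% limit | Share of 20% limit |
|---|---|---|
| 5 | 5/30 = 17% | 5/60 = 8% |
| 10 | 10/30 = 33% | 10/60 = 17% |
| 15 | 15/30 = 50% | 15/60 = 25% |

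**2. Effect on a decision, with a 15-micron offset.** For a 300-micron baseline, extend covers 270 to 330, maintain covers above 330 to 360 or below 270, and reduce covers above 360.
- Upward: a true 316 (16/300 = +5.3%, extend) reads 331 (31/300 = +10.3%, maintain). A true 346 (46/300 = +15.3%, maintain) reads 361 (61/300 = +20.3%, reduce).
- Downward: a true 335 (35/300 = +11.7%, maintain) reads 320 (20/300 = +6.7%, extend). A true 280 (−20/300 = −6.7%, extend) reads 265 (−35/300 = −11.7%, maintain).

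Only eyes near a boundary change category, and the direction depends on the sign of the offset.

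**3. Whether the plan corrects itself.** A Secondary Baseline needs an improvement of more than 20% at three consecutive visits, which here means more than 60 microns. An upward offset can never trigger it, and a downward offset of 15 microns does not reach it alone. The old baseline would stay in use.

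**4. Effect on the thickness outcome.** This is measured from randomization, not from the Primary Baseline. If a fraction f of an arm's eyes has its randomization scan before an update and its follow-up scan after it, the mean change shifts by f × offset. With 10 microns, f = 1 gives 10 microns and f = 0.5 gives 5. A difference between two arms shifts by the offset times the difference in their fractions, so equal fractions cancel.

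**5. The change of term.** Following each rule through section 3.1:
- The 10% and 20% bands compare central foveal thickness with a central foveal thickness baseline, and they end at week 104.
- Central subfield thickness appears only from week 104, against a fixed 325, and is never compared with a stored foveal baseline.
- The thickness outcome is central foveal thickness at 12, 24 and 36 months.

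Any difference between the two quantities therefore takes up none of the bands and does not enter the outcome. It can reach the week-104 and year-3 injection decisions and counts. Through them it can reach focal-laser eligibility, which requires at least 2 injections in the prior 90 days.

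**The case against.** The strongest reply is that nothing is shown to have gone wrong. The protocol permits a software change but does not say that one will be installed during follow-up, and it gives no evidence that an update alters the thickness reading. The device is fixed and every scan is archived, so later re-processing is not ruled out. The offsets above are assumed. All of this stands, and it limits the point to a preventable risk of unknown size. It does not remove the point. Archiving helps only if someone is told to re-process, and interval decisions are made at the visit, before any later correction.

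OCT is also not the only driver of treatment. A loss of more than 15 letters resets the interval, the three-injection series after week 52 ignores OCT, and a year-3 loss of more than 5 letters leads to treatment regardless of thickness. That is correct and narrows the exposure.

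On the two terms, a reader might infer that the measurement itself switches at week 104, that the switch eats into the 10% band, or that it biases the thickness outcome. The documents support none of these. They show a change of name between undefined terms, and the authors may have meant one value throughout. The sponsor may equally intend different quantities for different rules. Step 5 of the working shows why the bands and the outcome are out of reach.

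**Conclusion.** The software point holds as an inexpensive improvement. The stated rule allows version drift between an eye's stored baseline and its later scans. Up to week 104 such drift could alter injection intervals in TREX and GILA but not in Monthly. It could also shift thickness change, but only for eyes whose scans straddle an update. Its size cannot be taken from the documents. The 17%, 33% and 50% figures rest on assumed offsets of 5, 10 and 15 microns and a 300-micron baseline.

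The two thickness terms are a minor matter of definition, limited to the week-104 and year-3 decisions and what follows from them.

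It would be too strong to infer that the primary result is compromised. That outcome is visual acuity in weeks 92 to 107, mostly before the subfield term comes into use, so the term change has little bearing on it. Software drift could reach it only indirectly, through altered intervals. Power and alpha are unaffected.

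**What to change.** 1. In section 4.5.1, replace the instruction to use the newest software with one named Spectralis software and segmentation version, held fixed at all sites for the trial.
2. If an update is unavoidable, require that the eye's archived baseline and earlier scans be re-processed in the new version before any percentage or mean change is computed. State that the archive must keep data that can be re-processed, and record the version with each scan.
3. Define central foveal thickness and central subfield thickness by the Spectralis output that each rule uses, and reconcile the passages in sections 3.1 and 4.2 that attach 325 microns to them. The choice of quantity and cut-off is the sponsor's.

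The cost is a few lines of protocol text and an instruction to sites, plus either postponed vendor updates or some re-processing work. Sample size, visits and the analysis model do not change.
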